5.2 Exclusion Criteria

Participants are excluded from the study if any of the following criteria apply:

Medical Conditions

- 1 Hospitalisation for an acute cardiovascular event within 12 weeks prior to screening
- 2 Unable to take oral SZC drug mix
- 3 -
- 4 With a life expectancy of less than 6 months
- 5 Any medical condition that, in the opinion of the investigator makes the participant not suitable for inclusion
- 6 -
- 7 QT interval corrected by the Fridericia method (QTcF) $> 550 \text{ msec}$
- 8 History of QT prolongation associated with other medications that required discontinuation of that medication
- 9 Congenital long QT syndrome

10 Clinically significant arrhythmias as judged by the investigator

11 -

12 -

Prior/Concomitant Therapy

13 Ongoing treatment with SZC or patiromer before current ED visit/hospital admission (ongoing treatment with other K-binders before current ED visit/hospital admission is allowed). Note: Initiation of SZC or patiromer during the current ED visit/hospitalisation preceding enrolment is allowed.

14 Chronic haemodialysis or peritoneal dialysis or the recipient of or scheduled date for a kidney transplant. Note: Emergency/unscheduled haemodialysis to treat HK during the current ED visit/hospitalisation preceding enrolment is allowed.

Prior/Concurrent Clinical Study Experience

15 Participation in another clinical study with an investigational medicinal product (IMP) administered during the month before screening.

16 Known hypersensitivity to SZC or any of the excipients of the product

Other Exclusions

17 Involvement in the planning and/or conduct of the study (applies to both AstraZeneca staff and/or staff at the study site)

18 Judgment by the investigator that the participant should not participate in the study if the participant is unlikely to comply with study procedures, restrictions, and requirements

19 Previous randomisation in the present study

20 For women only: Women of child-bearing potential (WOCBP; ie, those who are not chemically or surgically sterilised or who are not post-menopausal) who are not willing to use one of the methods of contraception described hereafter, or who are not stable on the contraception method for the last one month, from the time of signing the informed consent throughout the study and 7 days after the last dose:

- a) Combined (estrogen and progestogen containing) hormonal contraception associated with inhibition of ovulation: oral, intravaginal, transdermal
- b) Progestogen-only hormonal contraception associated with inhibition of ovulation: oral, injectable, implantable
- c) Intrauterine device
- d) Intrauterine hormone-releasing system
- e) Bilateral tubal occlusion
- f) Vasectomised partner (vasectomised partner is a highly effective birth control method provided that partner is the sole sexual partner of the WOCBP participant and that the vasectomised partner has received medical assessment of the surgical success

g) Sexual abstinence: it is considered a highly effective method only if defined as refraining from heterosexual intercourse during the entire period of risk associated with the study treatments. The reliability of sexual abstinence needs to be evaluated in relation to the duration of the study and the preferred and usual lifestyle of the participant.

21 For WOCBP only: Women who have a positive pregnancy test at screening OR women who are breastfeeding.

5.3 Lifestyle Considerations

No lifestyle restrictions are required in the study.

5.4 Screen Failures

Screen failures are defined as participants who consent to participate in the clinical study but are not subsequently entered in the study. A minimal set of screen failure information is required to ensure transparent reporting of screen failure participants to meet the Consolidated Standards of Reporting Trials publishing requirements and to respond to queries from regulatory authorities. Minimal information includes demography, screen failure details, eligibility criteria, and any serious adverse event (SAE) and should be recorded in the electronic Case Report Form (eCRF).

Individuals who do not meet the criteria for participation in this study (screen failure) may be rescreened (maximum twice) if:

- screen failure is due to not meeting K⁺ or eGFR inclusion criteria
- exclusion criteria are no longer applicable
- technical issues are encountered at enrolment site visit.

Participants who are rescreened should be assigned the same participant number as for the initial screening.

6 STUDY INTERVENTION

Study intervention is defined as any investigational intervention(s), marketed product(s) or placebo intended to be administered to or medical device(s) utilised by a study participant according to the study protocol.

6.1 Screening and Inpatient Phase

Participants with HK (see inclusion criterion #4) and not on SZC or patiromer before this current ED visit/hospital admission (initiation of SZC or patiromer during ED visit/hospitalisation preceding enrolment is allowed), will start SZC, as per local label, during the inpatient phase. Initiation of SZC treatment will be based on local measurement of K⁺, obtained within 24 hours prior to first dose of on-study SZC:

- Correction treatment: 10 g, TID for up to 72 hours. Typically, NK is achieved within 24 to 48 hours. If participants are still hyperkalaemic after 48 hours of treatment, the same regimen can be continued for an additional 24 hours. If NK is not achieved after 72 hours of treatment, other treatment approaches should be considered, and the participant discontinued from the study due to lack of SZC effect. Participants who received any HK treatment during current ED visit/hospitalisation preceding enrolment and are NK at baseline can directly start the maintenance dose of SZC (see hereafter).
- Maintenance treatment (once NK [K^+ between 3.5 and 5.0 mmol/L, inclusive] is reached): 5 g, QD. Dose will be adjusted based on K^+ (see [Table 4](#)). The recommended maintenance dose range is from 5 g every other day to 10 g daily.

Participants with NK and who have been started on a maintenance dose for SZC (per local label) at the time of discharge will be randomised at discharge to either Arm A (SZC per local label) or Arm B (SoC, as per local practice) and enter the outpatient phase.

The following participants will not be eligible for randomisation:

- Participant intended to be discharged on a K-binder as per the site routine medical practice (discontinued from the study)
- Participant with an in-hospital phase exceeding 21 days (including screening), except when study medical monitor's approval was sought for longer duration of hospital stays for specific participants
- Participants with $K^+ > 5.0$ mmol/L at discharge; these participants will be discontinued from the study treatment and followed up as per protocol
- Participants with $K^+ < 3.5$ mmol/L at discharge; these participants will be discontinued from study treatment and will be followed per protocol.

6.2 Outpatient Phase

Participants randomised to Arm A will be discharged with SZC dosed per local label (from 5 g every other day to 10 g daily) to manage K^+ until the EOT (180 days post-discharge).

As per label, SZC dose titration will be allowed based on K^+ levels as detailed in [Table 4](#).

Table 4 Dose Titration and Discontinuation Criteria During the Outpatient Phase

K^+ (mmol/L)	Dose Titration and Discontinuation Criteria for Abnormal K^+
< 3.0	
• Treatment permanently discontinued (see Section 7.1.1). Check ECG and treat according to medical judgment.
3.0 - 3.4	
• Check ECG, permanently discontinue treatment if serious arrhythmia found and treat according to medical judgment.

K⁺ (mmol/L)	Dose Titration and Discontinuation Criteria for Abnormal K⁺
	
 • If no serious arrhythmia found, investigator to consider to down-titrate^a or pause SZC and treat according to medical judgment. Participants with heart failure should pause study drug. • Increase monitoring until K⁺ \geq 3.5 mmol/L.^a • Evaluate for underlying risk for hypokalaemia. If hypokalaemia resolves and participant deemed appropriate to restart treatment (for participants who have paused SZC), then the investigator should consider to restart SZC at a lower dose.^a
3.5 - 5.0	
 • No change in SZC dose is recommended.
5.1 – 5.5	
 • Increase SZC dose by 5 g QD increments up to a maximum of 10 g QD.^a • Increase monitoring until K⁺ in normal range.
5.6 – 6.0	
 • Check ECG, discontinue treatment if serious arrhythmia found and treat according to medical judgment. • If no serious arrhythmia, increase SZC dose by 5 g QD increments up to a maximum of 10 g QD.^a • Further K⁺ monitoring and treatment per investigator medical judgment based on participant risk and benefit. • Increase monitoring frequency until K⁺ in normal range.
> 6.0	
 • Treatment permanently discontinued (see Section 7.1.1); initiate rescue therapy (see Section 6.7.1 for rescue therapy). • Check ECG and treat according to medical judgment.

Abbreviations: ECG = electrocardiogram; K⁺ = potassium; QD = once daily; RAASi = renin angiotensin-aldosterone system inhibitor; SZC = sodium zirconium cyclosilicate.

^a Any time study drug dose is adjusted, or if in either treatment arm, a concomitant medication which may affect K⁺ levels is changed (eg, use of RAASi or diuretics), the participant needs to return to the site 7 (\pm 2) days later for a K⁺ measurement and recording of adverse events and concomitant medications.

Participants randomised to Arm B will be discharged without SZC and will receive SoC per local practice for managing their K⁺ until the EOT (180 days post-discharge). The SoC will be at the discretion of the treating physician; however, participants intended to be discharged with a K-binder will not be randomised. However, participants in Arm B may have a K-binder prescribed at Day 7 post-discharge (or after Day 7 post-discharge) to treat confirmed HK or in case there is an increase in K⁺ level since discharge that, in the investigator's opinion, requires therapy.

The K⁺ levels will be measured at on-site visits at Days 7 (local laboratory), 90 (local and central laboratories), and 180 (local and central laboratories) (see Sections 8.1.1 and 8.2.4). Overall monitoring frequency will depend upon a variety of factors including other medications, progression of CKD, and dietary K⁺ intake. It is the responsibility of the treating physicians to check the participant K⁺ as medically appropriate/in accordance with the label (for both SZC and SoC arms). In addition to the scheduled on-site visits, participants should return to the site for a local K⁺ measurement 7 (\pm 2) days after any dose adjustment to SZC.

Additionally, participants in either treatment arm should have their K⁺ measured locally 7 (\pm 2) days after changes are made to medications that affect K⁺ levels (eg, use of RAASI or diuretics).

Such additional K⁺ checks and site visits will take place as clinically indicated and the resulting data, including AEs and concomitant medication information, relating to these visits will also be collected during the study.

6.3 Study Interventions Administered

6.3.1 Investigational Products

Table 5 provides information on the IMP.

Table 5 Investigational Products

Intervention Name	Sodium zirconium cyclosilicate (SZC)
Dose Formulation/Unit Dose Strength	White to grey crystalline powder for oral suspension in 5 g sachets
Route of Administration	Oral
Use	Investigational product
Sourcing	Provided centrally by the sponsor
Packaging and Labeling	Study treatment will be provided in sachets. Each sachet will be labeled in accordance with Good Manufacturing Practice Annex 13 and per country regulatory requirement. Label text will be translated into local language.

During the inpatient phase, SZC will be dispensed daily to all participants.

During the outpatient phase, SZC will be supplied, at the site, to the participants randomised to Arm A at the timepoints indicated in the SoA ([Table 1](#)), in the amount expected to account for its usage as per the investigator's prescription, including possible dose modifications that might occur before the next scheduled dispensation visit. Sodium zirconium cyclosilicate may also be dispensed at unscheduled visits. Home delivery may be considered as alternative mode of supplying drug where local regulations allow.

For each participant, the investigator will select the SoC treatment (based on the most appropriate option for the participant) that the participant would receive if randomised to the SoC arm prior to randomisation of the participant. This must be completed for all participants.

The information will be recorded in the Interactive Response Technology/Randomisation and Trial Supply Management (IRT/RTSM) system.

6.4 Preparation/Handling/Storage/Accountability

The oral suspension to be administered to participants during the inpatient phase of the study should be prepared in the following way: the entire contents of the sachet should be emptied in a drinking glass containing approximately 45 ml of water and stirred well. The tasteless liquid should be drunk while still cloudy. The powder will not dissolve. If the powder settles, the liquid should be stirred again and taken. If needed, rinse the glass with more water to ensure that all of the content is taken. If 2 sachets (total dose of 10 g) are needed, the same volume of water (45 ml) should be used (ie, no increase in volume of water).

The investigator or designee must confirm appropriate temperature conditions have been maintained during transit and storage for all study intervention received and any discrepancies are reported and resolved before use of the study intervention.

Only participants enrolled in the study may receive study intervention and only authorised site staff may supply or administer study intervention. All study intervention must be stored in a secure, environmentally controlled, and monitored (manual or automated) area in accordance with the labelled storage conditions with access limited to the investigator and authorised site staff.

The investigator, institution, or the head of the medical institution (where applicable) is responsible for study intervention accountability, reconciliation, and record maintenance (ie, receipt, reconciliation, and final disposition records).

Further guidance and information for the final disposition of unused study interventions will depend on local regulations in a given study country.

6.5 Measures to Minimise Bias: Randomisation and Blinding

This is an open-label study; however, the specific intervention to be taken by a participant will be randomly assigned using an IRT/RTSM. Before the study is initiated, call-in directions for the IRT and/or the log-in information and directions for the RTSM will be provided to each site. The site will contact the IRT/RTSM prior to the start of study intervention administration for each participant. The site will record the intervention assignment on the applicable eCRF, if required. Once a randomisation number has been assigned it must not be re-assigned.

Potential bias will be reduced by central randomisation.

Study intervention will be dispensed at the study visits summarised in the SoA (Table 1) and may also be dispensed at unscheduled visits.

Dispensed but not used study intervention in unopened sachets may be re-dispensed to the

same or other study participants in the inpatient phase.

Returned study intervention in unopened packets or sachets may be re-dispensed to the same study participant during the outpatient phase.

6.6 Study Intervention Compliance

When participants are dosed at the site, which will occur during the inpatient phase, they will receive SZC directly from the investigator or designee, under medical supervision. The date, and time if applicable, of dose administered in the hospital will be recorded in the source documents and recorded in the eCRF. The dose of SZC and study participant identification will be confirmed at the time of dosing by a member of the study site staff other than the person administering the study intervention.

When participants self-administer study interventions at home (SZC or SoC), compliance with study interventions will be assessed at each visit (both on-site and telephone visits).

Compliance will be assessed by counting returned sachets and direct questioning during the visits and documented in the source documents and eCRF. Deviation(s) from the prescribed dosage regimen should be recorded in the eCRF and in the source documentation.

A record of the number of SZC sachets for SZC dispensed to and taken by each participant must be maintained and reconciled with study intervention and compliance records. Intervention start and stop dates, including dates for intervention delays and/or dose reductions or increases will also be recorded in the eCRF.

There will not be accountability for participants allocated to SoC.

6.7 Concomitant Therapy

Sodium zirconium cyclosilicate can transiently increase gastric pH by absorbing hydrogen ions that can lead to changes in solubility and absorption kinetics for co-administrated drugs with pH-dependent bioavailability. Therefore, SZC should be administered at least 2 hours before or 2 hours after oral medications with gastric pH-dependent bioavailability.

Examples of drugs that should be taken 2 hours before or after SZC to avoid possible raised gastric pH drug interaction are listed below:

Class of Drug	Drugs
Aazole antifungals	Ketoconazole, itraconazole, posaconazole
Anti-human immunodeficiency drugs	Atazanavir, nelfinavir, indinavir, ritonavir, saquinavir, raltegravir, ledipasvir, rilpivirine
Tyrosine kinase inhibitors	Erlotinib, dasatinib, nilotinib

Note, this list is not exhaustive. Please refer to the SmPC of concomitant medications the participant gets administered for pH dependent bioavailability.

Sodium zirconium cyclosilicate can be co-administered with oral medications that do not exhibit pH-dependent bioavailability without spacing of dosing times.

In a drug-drug interaction study in healthy volunteers, co-administration of S_ZC 15 g with tacrolimus 5 mg resulted in a decreased tacrolimus area under concentration curve and maximum observed plasma concentration by 37% and 29%, respectively. Therefore, tacrolimus should be taken at least 2 hours before or after S_ZC. In the same study, co-administration of S_ZC and cyclosporin did not show a clinically meaningful interaction.

Potassium binders will not be authorized in Arm A, unless they are prescribed as rescue therapy (see Section 6.7.1).

Any medication or vaccine (including over-the-counter or prescription medicines, vitamins, and/or herbal supplements) or other specific categories of interest that the participant is receiving at the time of enrolment or receives during the study must be recorded along with:

- Reason for use
- Dates of administration including start and end dates
- Dosage information including dose and frequency.

If the participant received one (or more) Coronavirus disease 2019 (COVID-19) vaccination(s) prior to enrolment, then this needs to be recorded in the eCRF.

The sponsor or contract research organization study physician should be contacted if there are any questions regarding concomitant or prior therapy.

6.7.1 Rescue Medicine

Rescue therapy is allowed and is at the discretion of the treating physician (see Table 4 for guidance for participants receiving S_ZC). For both arms, rescue therapy is defined as any therapeutic intervention considered necessary in accordance to local practice patterns to manage high K⁺ in the setting of severe HK as defined by the treating physician and site. This may include, but not limited to:

- 1) beta-adrenergic agonists
- 2) calcium gluconate
- 3) sodium bicarbonate
- 4) intravenous insulin/glucose
- 5) K-binders¹
- 6) any emergency dialysis or other forms of renal replacement treatments given with the goal of controlling the HK.

Rescue therapy should be followed by the appropriate SZC dose adjustment and proper documentation of the event.

The sponsor will not supply rescue therapy that will be obtained locally.

The date and time of rescue therapy administration, as well as the name and dosage regimen of the rescue therapy, must be recorded in the eCRF. Additionally, the adjudication committee will review reported concomitant medications to determine if any should be included as rescue therapy for HK.

Use of rescue therapy will be treated statistically as described in the statistical analysis plan (SAP). See Statistical Considerations, Section 9, for implications of the use of rescue therapy and/or other K-binders to the analysis of endpoints.

6.8 Dose Modification

For Arm A, see [Table 4](#) for SZC dose titration.

For Arm B, SoC will be adjusted at the discretion of the treating physician or the investigator.

¹ While participants intended to be discharged on a binder will not be eligible for randomisation, a binder may be needed as rescue therapy. Rescue therapy with binder is defined as the addition of any binder, excluding SZC, to Arm A or the addition of any binder, including SZC, to Arm B. The study is open label, ie, the investigator shall be aware of whether participants are treated with SZC. As per local practice, SZC should be withdrawn if and when another binder is initiated.

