9.4.3 Efficacy

9.4.3.1 Primary Endpoints

Occurrence (yes/no) of NK (K^+ between 3.5 and 5.0 mmol/L, inclusive) at 180 days post-discharge

- Population: FAS
- Endpoint: Occurrence (yes/no) of NK (K^+ between 3.5 and 5.0 mmol/L, inclusive) at 180 days post-discharge
- Intercurrent event strategy: Participants who discontinue treatment with a K^+ measurement at 180 days post-discharge will have this value used irrespective of treatment discontinuation (treatment policy strategy). Use of rescue therapy for HK will be considered to be non-response (composite variable strategy). The RAASI down-titration (including discontinuation) will be considered to be non-response (composite variable strategy). Participants who die of any cause prior to 180 days post-discharge or who are lost to follow-up for any reason will be considered to be non-response (composite variable strategy).
- Population level summary (analysis): Logistic regression analysis with response (occurrence) as the dependent variable and randomised treatment group as the

independent variable. The odds ratio along with the two-sided 95% confidence intervals and two-sided p-value (significance declared < 0.05) will be displayed.

Sensitivity Analyses

The analyses of the primary endpoint will be repeated by varying the estimand:

- Population level summary (analysis): Providing there are sufficient participants within each covariate to support the analysis, the logistic regression model will include randomised treatment group and the following baseline variables: age (as a spline), sex, presence of heart failure, diabetes, RAASi use, CKD stage, and baseline K⁺ (mild HK defined by K⁺ between > 5.0 and ≤ 5.5 mmol/L and moderate/severe HK defined by K⁺ between > 5.5 and ≤ 6.5 mmol/L) as independent variables.
- Intercurrent event strategy: As primary estimand, but participants needing rescue therapy for HK will follow the treatment policy strategy (ie, regardless of the intercurrent event).
- Intercurrent event strategy: As primary estimand, but participants with RAASi down-titration (including discontinuation) will follow the treatment policy strategy (ie, regardless of the intercurrent event).
- Intercurrent event strategy: As primary estimand but participants who die or are lost to follow-up prior to 180 days post-discharge will not be evaluated (completers analysis only).

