- The participant must be informed that his/her medical records may be examined by Clinical Quality Assurance auditors or other authorised personnel appointed by the sponsor, by appropriate IRB/IEC members, and by inspectors from regulatory authorities.

A 5 Committees Structure

An adjudication committee will be formed. This committee will be composed of independent nephrologists, blinded to study treatment assignment. The objective of this committee is to evaluate whether the hospital admissions or ED visits meet the pre-specified Charter definition of HK as contributing factor for these encounters. The committee will also review the reported concomitant medications to determine RAASi down-titration/discontinuation events and use of rescue therapy for HK.

A 6 Dissemination of Clinical Study Data

Any results both technical and lay summaries for this trial, will be submitted to EU CTIS within a year from global End of Trial Date in all participating countries, due to scientific reasons, as otherwise statistical analysis is not relevant.

A description of this clinical study will be available on <http://www.astrazenecaclinicaltrials.com> and <http://www.clinicaltrials.gov> as will the summary of the study results when they are available. The clinical study and/or summary of study results may also be available on other websites according to the regulations of the countries in which the study is conducted.

A 7 Data Quality Assurance

- All participant data relating to the study will be recorded on eCRF unless transmitted to the sponsor or designee electronically (eg, laboratory data). The investigator is responsible for verifying that data entries are accurate and correct by electronically signing the eCRF.
- The investigator must maintain accurate documentation (source data) that supports the information entered in the eCRF.
- The investigator must permit study-related monitoring, audits, IRB/IEC review, and regulatory agency inspections and provide direct access to source data documents.
- Monitoring details describing strategy (eg, risk-based initiatives in operations and quality such as Risk Management and Mitigation Strategies and Analytical Risk-Based Monitoring), methods, responsibilities and requirements, including handling of noncompliance issues and monitoring techniques (central, remote, or on-site monitoring) are provided in the Monitoring Plan.

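### The rescue footnote has no severity condition, so a permitted, non-severe binder start in the SoC arm can be counted as a primary failure and a main-secondary event

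*Protocol*

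**What the plan says.** **Rescue, general definition.** Protocol 6.7.1 defines rescue for both arms as treatment needed to manage high potassium "in the setting of severe HK as defined by the treating physician and site". K-binders are item 5 of the list of examples and carry footnote 1.

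**Rescue, footnote.** For the SoC arm, binder rescue is "the addition of any binder, including SZC, to Arm B"; for the SZC arm, it is any added binder other than SZC. No severity or potassium threshold is stated in the footnote itself.

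**Ordinary binder use in SoC.** Protocol 6.2 says "participants in Arm B may have a K-binder prescribed at Day 7 post-discharge (or after Day 7 post-discharge) to treat confirmed HK". A second permitted ground is a rise since discharge that the investigator thinks needs therapy. Sections 1.1 and 4.1 say the same.

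**Similar potassium in Arm A.** For 5.1–5.5 mmol/L, and for 5.6–6.0 mmol/L without serious arrhythmia, Table 4 says "Increase SZC dose by 5 g QD increments up to a maximum of 10 g QD". The footnote does not count this as rescue.

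**Consequence for endpoints.** Rescue is non-response in the primary endpoint (Protocol 9.4.3.1; SAP 4.2.2.1), whatever potassium is measured later (SAP 3.3.1.4.1). It is an event in secondary #1 (Protocol 9.4.3.2; SAP 4.2.3.1). These two endpoints are first and second in the testing order (SAP Table 5).

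**Who decides.** An adjudication committee "blinded to study treatment assignment" reviews reported concomitant medications to identify rescue (Protocol 6.7.1 and Appendix A 5). SAP 4.2 leaves final classification to that committee under a separate charter.

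**The concern.** Two rules for the same act stand in one section, and no text settles which governs. If the footnote is taken at its word, a step that the protocol permits as routine SoC management becomes a failure on both lead endpoints, while the corresponding step in the SZC arm has no effect on either. Part of the arm difference would then come from the definition and not from potassium at Day 180, admissions or deaths. The trial is open label, the SoC binder decision is the investigator's, and the severity threshold is left to each physician and site, so the count could also vary between sites.

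**Working it through.** **1. The two readings applied to one case.** Take a participant in each arm with potassium of 5.3 mmol/L at Day 90 that the site does not regard as severe.

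- Arm A, dose below the Table 4 maximum: SZC is increased. This is not rescue on either reading and affects neither endpoint.
- Arm B: the investigator starts a binder, as 6.2 permits. On the literal footnote this is rescue: a primary non-responder even if normokalaemic at Day 180, and a secondary #1 event on the start date. If the footnote works only inside the severe-hyperkalaemia definition, it is neither.

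**2. The plan's own figures.** From Protocol 9.2.2, HR = ln(0.83)/ln(0.568) = 0.329. Freedman's formula gives (1.960 + 0.842)² × [(1 + 0.329)/(1 − 0.329)]² = 30.8, so 31 events. The mean event proportion is (0.17 + 0.432)/2 = 0.301, and 31/0.301/2 = 51.5, so 52 per arm. Then 104/0.8 = 130 randomised and 130/0.8 = 162.5, so 163 enrolled. The primary (0.88 v 0.59, no continuity correction) gives 36 per arm. All match. The secondary inputs are 16.2% + 0.8% = 17% and 40% + 3.2% = 43.2%. They contain no rescue events, so the sample size does not depend on which reading applies.

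**3. Effect of the literal reading on the primary.** Inputs: 130/2 = 65 per arm; the same true response p in both arms, set at each planning value in turn (0.59 and 0.88, Protocol 9.2.1); and an assumed share q of otherwise responding SoC participants who start a binder. Counted SoC response is p(1 − q). With d = pq and p̄ the mean of the two counted proportions, the chance of a significant result for SZC (two-sided 5%, two-proportion approximation) is Φ[(d − 1.96·se₀)/se₁], where se₀ = √[2p̄(1 − p̄)/65] and se₁ is the unpooled standard error.

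Example, p = 0.59 and q = 10%: d = 0.059, se₀ = 0.0871, se₁ = 0.0869, so Φ(−1.28) = 9.9%.

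| True NK, both arms | q | Counted SoC NK | Chance of significance for SZC |
|---|---|---|---|
| 0.59 | 10% | 0.531 | 9.9% |
| 0.59 | 20% | 0.472 | 26.9% |
| 0.88 | 10% | 0.792 | 27.1% |
| 0.88 | 20% | 0.704 | 70.0% |

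**4. Effect on secondary #1.** Simulated log-rank test with 65 per arm and 3,000 trials per setting. Other events are exponential with the same 180-day proportion e in both arms. SoC binder starts are added from Day 7 so that a share q of those otherwise event-free has started by Day 180. Counted SoC events are 1 − (1 − e)(1 − q). With q = 0 the simulation gives 2.4% (e = 17%) and 2.2% (e = 43.2%), close to the nominal 2.5%.

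| True events, both arms | q | Counted SoC events | Chance of significance for SZC |
|---|---|---|---|
| 17% | 10% | 25.3% | 20.1% |
| 17% | 20% | 33.6% | 59.4% |
| 43.2% | 10% | 48.9% | 9.5% |
| 43.2% | 20% | 54.6% | 25.2% |

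Simulation error is at most about 0.9 percentage points (one standard error).

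**5. What is already planned.** SAP 4.2.2.5 has a primary analysis with rescue under treatment policy. SAP 4.2.3.5 has covariate-adjusted, per-protocol, RAASi-censored and inverse-probability-weighted analyses of secondary #1, but none that changes the handling of rescue.

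**The case against.** The strongest reply is that the footnote never leaves the severe-hyperkalaemia definition. It is attached to an item in that list, opens by saying that a binder may be needed as rescue, and then says which binders qualify. Other text keeps ordinary binder use apart from rescue: 6.7.1 refers to rescue and/or other binders; 2.3.1 calls a Day 7 SoC binder start an adjustment and mentions binder rescue separately for the SZC arm; and exploratory endpoints #9–#11 (binder use) are distinct from #12 (rescue). This stands. A reader might infer that every SoC binder start will be counted as a failure; the documents support only that it can be.

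A reader might also infer that a committee blind to arm cannot apply a rule under which SZC counts only in Arm B. That goes too far. The committee works from reported concomitant medications, which are recorded with a reason for use (6.7), while Arm A SZC is study drug accounted for separately (6.3.1, 6.6). A workable blinded rule is conceivable. Whether the charter contains one is unknown.

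Excluding SZC from rescue in Arm A is not itself a defect, because SZC is the assigned treatment there. Counting a binder start as failure of a discharge strategy without a binder is also a legitimate composite choice if it is intended and stated. Nor is such a start empty of information, since it follows hyperkalaemia or a rise judged to need therapy.

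Finally, secondary #1 is not without context. Secondary #2 does not count rescue as an event, though it censors at rescue (SAP 4.2.4.1). Secondary #3 counts admissions and hyperkalaemia-related ED visits with rescue under treatment policy (SAP 4.2.5.1), and exploratory #12 isolates rescue. These would help to reveal a result driven by binder starts. None re-analyses the main composite with binder starts removed.

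**Conclusion.** The rescue definition is ambiguous on a point that feeds both lead endpoints, and the ambiguity runs in one direction, against SoC. The size depends on the literal reading being applied, on no true treatment effect, on no rescue in Arm A to offset it, and on an assumed 10–20% of otherwise successful SoC participants starting a binder. Under those conditions the chance of a significant result favouring SZC is about 10–70% for the primary and 10–59% for secondary #1, against a nominal 2.5%; the spread reflects the assumed base rates. The documents give no post-discharge SoC binder rate. The 0.1% in Protocol 2.2 concerns binders received at discharge in the US. The primary figures use a two-proportion test in place of the SAP's country-adjusted logistic model, and the secondary simulation has no loss to follow-up. They illustrate sensitivity to the definition and do not forecast the trial.

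A reader might take this to mean that the sample size is wrong. It is not: 52 per arm and 36 per arm both reproduce. On the severe-only reading, a non-severe binder start counts against neither arm and this source of bias disappears.

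**What to change.** 1. Reconcile Protocol 1.1, 4.1, 6.2, the body of 6.7.1, footnote 1 and the adjudication charter. One endpoint definition of rescue therapy for hyperkalaemia should apply in both arms and be usable by a committee that does not know the arm. Which definition is for the sponsor to choose.
2. In SAP 4.2.3.5, add a sensitivity analysis of secondary #1 in which a binder start alone is not an event and follow-up continues to the next component.
3. In SAP 4.2.2.4, split rescue in the non-response sub-table into binder and other rescue, by arm.

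The cost is a protocol and charter clarification, one extra analysis and one extra table split, settled before database lock. The downside is possibly fewer SoC events in secondary #1; the planned event proportions contain none from rescue, so the stated sample size does not rely on them.
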